3.12. Handling of missing data & dropouts

Given that this is an uncontrolled pilot study, its principal aim is to assess the feasibility and acceptability of the ESTAIR manual. We will therefore closely monitor dropout rates and conduct follow-up with individuals who withdraw from the intervention. During follow-ups we will also try to encourage participants to continue treatment. We will also conduct feedback interviews, when possible, with drop-outs, to understand reasons for dropout and have accurate representation of the feasibility and acceptability of our intervention.

Regarding statistical analyses, we will not be imputing missing data. Only participants who underwent assessment at both the pretest and post-test will be included in the analysis.

4. Ethical Considerations

Our participants are from a highly vulnerable population. This will require culturally sensitive and clinically trained professionals. To anticipate this, our research team consists of local experts, such as [name], who is highly experienced in trauma care clinical settings, as well as researchers. We also have [name], who has over 10 years of training professionals and experience working with vulnerable populations. We have connections to public and private hospitals in case of emergencies. All psychotherapists are also trained and have experience working with clients with severe mental health disorders and trained in this manual. [name], UniL Supervisor has connections with therapy developers in case any changes or accommodations to treatment is needed. This way we have local and international support of experts to ensure that we provide the best care for participants.

Other ethical considerations include the voluntary nature of participation in the project. Given the strain on public services in Egypt, the difficulty in accessing care, and the need for out-of-pocket payments, participation in our study may be the only affordable option for certain participants to receive

appropriate psychotherapeutic care. This may act as a strength in offering an additional option for care, but it may also be an ethical consideration. Our study offers them a standardized intervention that is based on and supported by evidence as an effective treatment for CPTSD, which is a better option than existing care options.

Finally, due to constraints in budget and time, not all participants will be able to complete all four modules. Instead, some participants will only receive three modules. This raises an ethical concern regarding the need to ensure equal benefits for all participants. In module 4 of narrative exposure therapy, the focus is primarily on addressing symptoms of PTSD. The other three modules, on the other hand, are designed to target the symptom clusters associated with CPTSD and have been the main focus of cultural adaptation efforts. Thus, to the best of our ability and within the limitations at hand, every participant—including those who were not selected for module 4—receives a thorough intervention designed to improve functioning, reduce symptoms of CPTSD, and promote general well-being.

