Supervision: During the 18-week intervention, weekly preparatory and peer-supervision meetings will be held. In-training therapists will have weekly supervision with [name] from AUC faculty. The whole team will also receive supervision from an experienced psychiatrist and psychotherapist with over 10 years of clinical and supervision expertise in third-wave cognitive-behavioral therapy modalities in group and individual formats (twice a month). This supervision model and team triangulation method ensure the quality and appropriateness of the intervention, as well as the ethical conduct of the students throughout their participation.

Following each therapeutic module, participants will complete an assessment including all outcome measures (see Section 3.10). Assessments will be conducted by either therapists or co-facilitators. Participants will also participate in a short qualitative interview in group format to provide their feedback on each module of the manual. Feedback interviews will be conducted by graduate (master-level) RAs. Initial baseline assessments will be administered by NH, who possesses a Citi training certificate, during the months of July and August. The T1, T2, and T3 assessments, which will be carried out by an RA(s), will not commence until September 21st 2025. Recruitment of the RAs has not yet taken place; however, it is scheduled to occur within the next month. After the recruitment of the RA, they will complete the Citi training and subsequently provide their certificate to the IRB prior to commencing any assessment activities. Please see Appendix 8 for sample patient feedback interview guide for module 1 & 2; provided are guides in English, once finalized guides will be translated in Arabic. Feedback focus groups will be audio recorded. For each assessment and feedback session participants will receive 700 EGP as compensation.

Therapists and co-facilitators will fill out a fidelity check form after each session, to retain information regarding the implementation, process evaluation, and acceptability of the intervention. Please see Appendix 4 for the fidelity form. Based on these forms, RAs will then conduct debriefing focus group discussions with therapists and co-facilitators after each module. Feedback from patients and therapists, will be used to make final adaptations in the adapted ESTAIR manual.

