3.9. Withdrawal & discontinuation

Participants can withdraw at any time during the interviews, without providing any reason. It is also expected in such trials that participants will drop out with giving notice.

In the event of an immediate threat of suicide or the presence of severe psychotic symptoms, participants will be removed from the study. Should these symptoms appear, the therapy will be suspended, and the participants will be guided by therapists towards appropriate services to facilitate the required clinical measures for recovery, such as crisis intervention, medication, and, if deemed necessary, hospitalization. See Section 4.2 in adverse events and see appendix 6 for emergency services list. In such cases the case of the participant will be discussed in team supervision meetings, which include a consultant psychiatrist, 2 clinical psychologists, and 3 counselling psychologists).

Data collected until that time point will be used, unless the participant requests destruction of his data.

Participants will be substituted if they drop out early (i.e. before the introductory group session before module 1 sessions begin).

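### The plan follows up people who stop therapy but does not provide for inviting them to the post-assessment, so the secondary pre-post results will mainly describe those who stayed

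*Combined protocol and SAP*

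**What the plan says.** Section 3.12 says the team will "closely monitor dropout rates and conduct follow-up with individuals who withdraw from the intervention", will encourage them to continue, and adds: "We will also conduct feedback interviews, when possible, with drop-outs, to understand reasons for dropout". It mentions no outcome scale for that contact.

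Outcome measurement is tied to progress through therapy. Section 3.8 states: "Following each therapeutic module, participants will complete an assessment including all outcome measures". Its schedule tables place the post-assessment after the final session, in week 19 (three-module plan) or week 26 (four-module plan).

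On use of the data, section 3.12 says "Regarding statistical analyses, we will not be imputing missing data" and "Only participants who underwent assessment at both the pretest and post-test will be included in the analysis". Section 3.9 says of people who leave or are removed: "Data collected until that time point will be used, unless the participant requests destruction of his data". It is silent on data after that point. People who leave after the introductory session are not replaced (3.9). No sensitivity analysis for drop-outs is described.

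**The concern.** Initial impact on clinical outcomes is a declared aim (section 2). Section 3.11 examines it with one-sided paired tests and a judgement of clinically significant change for each participant. Both need a post-test. If people who stop therapy are not invited to give one, both results depend on having stayed, and stayers may differ from leavers in how much they changed.

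The plan intends to speak to these people anyway, and the scales are short self-report instruments. A post-test that is never requested cannot be replaced at the analysis stage, so the decision has to be made before follow-up. Section 11 presents the pilot as preparation for a powered randomised trial. That trial will also need to know whether people off therapy will still give outcome data.

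**Working it through.** The plan gives no figure for this bias, so there is none to reproduce. The check has three steps.

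**1. How many could be absent.** The sample is 20 (section 3.6). Section 3.11 grades completion in bands running from 60% to 90%. Applied to 20, this gives 0.90 × 20 = 18 to 0.60 × 20 = 12 completers, so 2 to 8 people without a post-test.

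**2. How far the estimate could move.** Section 3.11 gives one effect size, 0.24. Its type is not stated; it is taken here as a standardised paired change and assigned to stayers. The documents give no value for stoppers, so a range is used.

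- Mean over all 20 = p × 0.24 + (1 − p) × d, where p is the completion proportion and d the stoppers' change.
- Stayers-only estimate = 0.24.
- With d = 0 and half the stoppers returning (and resembling those who do not return), estimate = 0.24 × c / (c + r), where c is the number of completers and r the number returning.

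| Completion | c | Mean over all 20, d = 0 | Stayers-only ÷ that mean | Half of stoppers return | Mean over all 20, d = −0.24 |
|---|---|---|---|---|---|
| 90% | 18 | 0.216 | 1.11 | 0.24 × 18/19 = 0.227 | 0.192 |
| 80% | 16 | 0.192 | 1.25 | 0.24 × 16/18 = 0.213 | 0.144 |
| 70% | 14 | 0.168 | 1.43 | 0.24 × 14/17 = 0.198 | 0.096 |
| 60% | 12 | 0.144 | 1.67 | 0.24 × 12/16 = 0.180 | 0.048 |

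If d = 0.24, the mean over all 20 is 0.24 at every completion rate and there is no bias.

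**3. What a fix would gain.** Exact noncentral-t power for a one-sided paired test at 0.05 with effect 0.24 is 0.19 at n = 12, 0.25 at n = 18 and 0.27 at n = 20. About 109 pairs would be needed for 80% power. Recovering post-tests therefore improves how well the result represents all participants and hardly changes power.

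**The case against.** Several points against this have force.

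- **Silence is not prohibition.** A reader might infer that drop-outs are barred from the questionnaires or from the analysis. The documents do not say so. The 3.12 rule depends on being assessed twice, not on finishing therapy, so someone who stopped therapy but attended the post-assessment would be included as the text stands. The sentence in 3.9 governs data already collected. What stands is that no invitation is planned.
- **The existing contact is not a post-test.** A reader might infer that the missing scores could simply be taken at the drop-out interview. That contact follows withdrawal. For someone who leaves by week 6, it could come 19 − 6 = 13 weeks or more before the post-assessment. Interviews also happen only when possible, and people may leave without giving a reason.
- **The direction is plausible, not established.** Section 4.1 expects 5% to 10% of patients to deteriorate during treatment, but calls this temporary and does not link it to leaving. Section 3.9 does link some exits to a poor clinical state, but those people are removed from the study.
- **Some data on leavers will exist.** Those who finish a module before leaving have intermediate scores, which the multilevel models in 3.11 could use. A reader might infer that nothing can be known about leavers; that goes too far. However, the 3.12 restriction is worded for the statistical analyses in general. Read literally, it would also drop these scores from the models, which sits badly with 3.9.
- **The stakes are moderate.** These outcomes are secondary, section 3.1 disclaims conclusions on efficacy, and section 3.11 admits low power. The shift with d = 0 is 0.24 − 0.216 = 0.024 SD to 0.24 − 0.144 = 0.096 SD. The standard error of a mean change, in units of the SD of change, is 1/√18 = 0.24 to 1/√12 = 0.29, so sampling error is larger than the bias shown.

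These points limit the weight of the concern. They do not close the gap in the procedures.

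**Conclusion.** The point holds as a gap in planned data collection. Sections 3.8 to 3.12 provide for contacting people who stop therapy but not for inviting them to the post-assessment. With the two-assessment rule and no imputation, the pre-post tests and individual change counts will mainly describe stayers, with 2 to 8 of 20 potentially absent.

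The possible overstatement is a factor of 1.11 to 1.67. This rests on two assumptions: that 0.24 is a standardised paired change applying to stayers, and that stoppers do not change. It is larger if stoppers worsen and nil if they change as stayers do. Without their scores the report could not tell which.

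The primary completion percentage is unaffected. Because the affected outcomes are secondary and efficacy claims are disclaimed, this is a worthwhile, inexpensive improvement and not a flaw that undermines the pilot.

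**What to change.** In sections 3.9 and 3.12, state that stopping therapy is not the same as leaving outcome assessment. Then:

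1. Invite everyone who stops therapy, has not withdrawn consent to contact and was not removed from the study under 3.9 to complete the same scales at the scheduled post-assessment, week 19 or 26. Say which week applies to someone who leaves before the Module 4 places are filled.
2. Include them in the pre-post analysis. The 3.12 rule already allows this.
3. Report how many post-tests came from people off therapy and how many invited people declined. Do not count return for the scales alone as completion in the primary outcome.

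The cost is a few sentences of protocol text and a check that the consent form covers the later contact. Section 3.8 sets the payment: "For each assessment and feedback session participants will receive 700 EGP as compensation". For 2 to 8 people that is 2 × 700 = 1,400 to 8 × 700 = 5,600 EGP if all return. The scheduled week may require one contact separate from the drop-out interview. Some will decline or be unreachable, and those removed under 3.9 remain outside, so the possible bias is reduced and not eliminated.

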3.11. Data Analysis

Statistical analysis plan

For primary outcomes: We will primarily assess feasibility by determining the percentage of participants who complete the study until the end (among those who sign the informed consent). Based on reported dropout rates from studies using similar modular interventions with trauma survivors, we will consider 80-90% participation and adherence as excellent, 70-80% as satisfactory, and 60-70% as acceptable [42, 77].

We will assess the ITI feasibility, using the same method based on the percentage of participants who complete the ITI; 80-90% participation and adherence is considered as excellent, 70-80% as satisfactory, and 60-70% as acceptable.

In addition, we will calculate the mean and standard deviation of completion rates to offer more detail into the variation in adherence.

For secondary outcomes: Descriptive statistics will be calculated for demographic information and baseline characteristics of participants. For clinical outcomes, we will analyze changes in PTSD symptomatology and other clinical outcomes (e.g., depression, anxiety, somatic symptoms, and well-being) at the four or five measurement points depending on group allocation. (See section 3.8 procedures). We will use intermediate assessments after each module to statistically describe the participants' state (means, standard deviations, correlations), enhancing our understanding of the effects of intervention components.

Next, we will use pre-post comparisons based on data from the first and last assessments to establish the status of change (clinically significant change) for each participant. We will conduct one-

sided paired measures Student's t-tests at the group level. The null hypothesis (H0) is that the change is zero. The alternative hypothesis (H1) is there will be a decrease in symptoms of CPTSD, depression, anxiety, and somatization; and an increase in rates of wellbeing. Student's t tests will be conducted with a significance level of 0.05. If the assumptions for the Student's t test are not satisfied, we will utilize non-parametric tests, specifically the Wilcoxon test for paired measurements.

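### Section 3.12's pretest-and-post-test rule has no stated scope; read as written it also covers the multilevel models, where it sets aside usable scores (minor)

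*Combined protocol and SAP*

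**What the plan says.** Section 3.12 contains the plan's general rule on missing data. It first states "Regarding statistical analyses, we will not be imputing missing data" and then "Only participants who underwent assessment at both the pretest and post-test will be included in the analysis". No analysis is named and no exception is made.

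Section 3.11 plans several analyses of the clinical outcomes. Change is to be analysed "at the four or five measurement points depending on group allocation". The visits between modules have a purpose of their own: "We will use intermediate assessments after each module to statistically describe" how participants are doing. First and last assessments are compared, both for each person's change status and by one-sided paired t-tests, with a Wilcoxon test as fallback. Multilevel linear models then follow progress through therapy, with covariates explored.

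Section 3.8 has all outcome measures completed after each module. Section 3.9 expects attrition ("It is also expected in such trials that participants will drop out") and provides for removal: "In the event of an immediate threat of suicide or the presence of severe psychotic symptoms, participants will be removed from the study". On the scores already held it says: "Data collected until that time point will be used, unless the participant requests destruction of his data".

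**The concern.** The inclusion rule fits a comparison of two time points. It does not fit a longitudinal model, which can use a baseline and one or two post-module scores from someone never seen at post-test. Section 3.12 introduces the rule by referring to statistical analyses in the plural and does not limit it. An analyst following the text would therefore fit the multilevel models to completers only.

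Two things are at stake. If missing the post-test is related to scores already recorded, a completers-only model gives a biased picture of change that a model using all recorded scores would largely avoid. If it is unrelated, a little precision is lost. The team also cannot tell how to treat a participant removed under Section 3.9. Such a person's earlier scores are to be used under 3.9 but are left out under 3.12 unless a post-test is still obtained, and the plan neither promises nor rules out a post-test for people who leave therapy.

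**Working it through.** **1. Which analyses need a post-test.**

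| Analysis in Section 3.11 | Needs both pretest and post-test? |
|---|---|
| Paired t or Wilcoxon tests | Yes |
| Individual pre-post change status | Yes |
| Post-module descriptives | No |
| Multilevel models | No |

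**2. Scores set aside.** The Section 3.8 schedules place assessments at weeks 0, 6, 12 and 19 (3-module plan) or 0, 6, 12, 17 and 26 (4-module plan). A participant without the last one has 1 to 3, or 1 to 4, recorded assessments.

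Suppose all 20 participants start on the 3-module plan, so 20 × 4 = 80 assessments are scheduled, and k of them have no post-test. The rule sets aside between k and 3k assessments. The largest share of those actually recorded is 3k / [3k + 4(20 − k)].

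| k | Set aside | Share of 80 scheduled | Largest share of recorded |
|---|---|---|---|
| 2 | 2–6 | 2.5–7.5% | 6/78 = 7.7% |
| 4 | 4–12 | 5–15% | 12/76 = 15.8% |
| 8 | 8–24 | 10–30% | 24/72 = 33.3% |

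The values of k are illustrative. They apply the 90%, 80% and 60% edges of the feasibility bands to 20 starters, which is an assumption.

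**3. Bias in modelled change at week 19 (simulation, all inputs assumed).** Score = u0 + (−0.4 + u1)·t + e, with t = week/19 and lower scores meaning fewer symptoms. SD(u0) = 0.8 and SD(e) = 0.6, so the baseline SD is √(0.64 + 0.36) = 1. SD(u1) = 0.3 or 0.5. There were 60,000 subjects, 60% on the 3-module and 40% on the 4-module schedule; the plan's 5–10 of 20 is 25–50%. The log-odds of leaving after a visit is a + s·x, with s = 0.5 or 1.0 and a set so that 10%, 20% or 40% lack a post-test. A random intercept-and-slope model was fitted by maximum likelihood to completers and to all recorded scores. Each was compared with the same model on the full data. Biases are in baseline SDs.

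| Leaving depends on x = | Completers only: 10% / 20% / 40% lost | All recorded scores |
|---|---|---|
| nothing | within 0.002 | within 0.002 |
| recorded worsening | improvement overstated by 0.01–0.03 / 0.02–0.06 / 0.05–0.12 | within 0.005 |
| recorded improvement | improvement understated by 0.01–0.03 / 0.03–0.06 / 0.05–0.13 | within 0.005 |
| last recorded score level | at most 0.02, either direction | within 0.005 |
| unrecorded individual trend | 0.01–0.19 over the three loss rates | 0.01–0.16 |

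In the last row the all-data model repairs only about 16–25% of the bias. In the worst case the repair is 1 − 0.161/0.194 = 17%.

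**4. Precision with 20 people.** With the same variances, SE = √{[(Σ X′V⁻¹X)⁻¹]₂₂}, where V = XGX′ + 0.36·I. Leaving is unrelated to scores, the last visit is uniform over the non-final visits, and 5 people are on the 4-module plan.

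| Without post-test | SD(u1) | SE, completers | SE, all scores | Gain |
|---|---|---|---|---|
| 2 of 20 | 0.3 | 0.186 | 0.183 | 1.3% (unrounded SEs) |
| 4 of 20 | 0.5 | 0.222 | 0.216 | about 3% |
| 8 of 20 | 0.5 | 0.257 | 0.239 | about 7% |

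Across the settings tried, the SE is 0.17–0.26. The largest bias in step 3 (0.194) arises with SD(u1) = 0.5 and 40% lost, where the matching SE is 0.257.

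**5. Post-module descriptives.** Neither set is safe for reading change over time. With the step 3 variances on the 3-module schedule, if high scorers leave, the change in raw visit means overstates improvement by 0.03–0.07, 0.07–0.14 and 0.15–0.28 SD at 10%, 20% and 40% lost; completers-only change is off by about 0.04 at most. If people leave after recorded change, the order reverses: visit means are off by less than 0.04, completers by up to 0.15.

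**The case against.** The strongest reply is that the authors meant the rule only for the pre-post comparison. Its wording echoes that comparison and refers to the analysis in the singular, while Section 3.11 separately commits to multilevel models and to every measurement point. This is a plausible reading, but nothing in the text confines the rule to it, and writing down the scope settles the matter either way.

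A reader might infer that Sections 3.9 and 3.12 contradict each other. They do not. Section 3.9 does not say what the data will be used for. It sits beside the right to have data destroyed, and it could be met through the feasibility percentage or interviews with those who leave. Tension is the right word.

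A reader might also take the 60–90% bands as the expected loss. They are ratings of completion among people who sign consent. Under Section 3.8 consent precedes the ITQ screen, and Section 3.9 adds: "Participants will be substituted if they drop out early". Some non-completers in that denominator would therefore never be starters without a post-test. The documents give no expected drop-out rate among starters.

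Nor does the 5–10% deterioration figure in Section 4.1 show that worsening participants leave. That section calls the deterioration temporary and does not link it to drop-out.

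**Conclusion.** The point holds as a minor one. The rule lacks a scope and, read as written, takes usable scores out of the multilevel models. It is not evidence that the trial's results will be materially biased. The primary feasibility percentage has its own denominator and is unaffected, power is acknowledged to be low, and Section 3.1 disclaims any conclusion on efficacy. What remains is the secondary description of initial impact.

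Under the assumed variances and drop-out mechanisms, the completers-only bias runs from essentially nil to 0.19 SD, below the matching standard error, and using all scores lowers the standard error by about 1–7%. The documents fix neither the size nor the direction of any real bias, because they do not say how many starters will leave or why.

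**What to change.** Reconcile Sections 3.9, 3.11 and 3.12 by stating the analysis set for each analysis:

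- The pretest-and-post-test rule applies only to the paired t or Wilcoxon tests and the individual pre-post change status.
- The multilevel models use all available assessments of every participant who started therapy and has a baseline, estimated by likelihood without imputation, under a stated missing-at-random assumption.
- Post-module descriptives show the number assessed at each visit. Because all-available and completers-only means can each mislead about change, present both or take change over time from the multilevel model.
- Requests for data destruction are honoured as Section 3.9 already provides.

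The cost is a few sentences, with no new data, staff or imputation. The downsides are reliance on missing at random and a small gain. The change does little for participants who leave before the week-6 assessment, who contribute only a baseline, or for departures driven by worsening that was never recorded.

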Participants will then be invited to a debriefing interview to provide us feedback on the ITI, including the module. Feedback interviews will be conducted by a (master-level) RA and will be audio-recorded. Please see Appendix 8 for sample patient feedback interview guide; provided are guides in English, once finalized guides will be translated in Arabic.

Participants will receive compensation of 700 EGP per session, for a total of three sessions (two ITI sessions and one feedback session).

Therapeutic program

The first three modules will be provided in a group, face-to-face setting in either AUC campus or other clinics (see Section 3.7). Due to clinical reasons, Module 4 (narrative exposure) needs to be delivered individually. Module 4 will take 5-7 sessions. Hence, due to budget constraints, only 5–10 participants will be chosen to complete the narrative exposure therapy component. We will ask participants if they are interested to conduct additional 4 sessions to enhance PTSD symptoms. We will ask one group at a time until the desired number is fulfilled.

It is expected that individuals who do not undergo the narrative exposure therapy module will still experience positive outcomes from the remaining components of the intervention, including improvements in symptoms of complex PTSD and overall functioning.

Participants will be divided into four groups. Each group will consist of five participants. Groups will be organized based on geographical preference of therapy and/or participant characteristics (e.g. gender or education level) to enhance group harmony and cohesiveness. Two psychotherapists, the applicant (who is a trained psychotherapist herself), and another psychotherapist, will be trained on using the manual and will lead group sessions. They will be assisted by two master-level psychotherapists in training. The graduate program committee in the counselling psychology program AUC agreed that two master's students could serve as co-facilitators as a part of their clinical internship.

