We will perform longitudinal analyses utilizing multilevel linear models. This will enable us to gain a deeper understanding of how participants' progress throughout the duration of psychotherapy. The multilevel models will enable us to examine the impact of additional variables, such as gender, type of trauma, or group allocation (i.e., number of sessions), in an exploratory manner.

Considering our limited sample size of 20 participants and the fact that similar interventions have shown an effect size of 0.24, we acknowledge that the lack of statistical power may prevent us from observing the effects of our intervention on clinical outcomes.

Statistics will be conducted by the same team that conducted the analysis of the parallel Swiss arm of the study (see Section 3.2 Research Team) and will be facilitated by the free software R [78]

Qualitative analysis

We will use framework analysis to extract the most important information related to acceptability from patient and therapists qualitative interviews [79]. We will use MAXQDA software to facilitate analysis [80]. Data will be transcribed and translated in Arabic by the applicant and research assistants, who are native speakers.

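### As worded, Section 3.12 restricts every clinical analysis to participants with both a pretest and a post-test, although only the paired comparisons need both and Section 3.9 says earlier data will be used

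*Combined protocol and SAP*

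**What the plan says.** Section 3.12 rules out imputation for the statistical analyses and continues: "Only participants who underwent assessment at both the pretest and post-test will be included in the analysis". No analysis is exempted.

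Section 3.11 plans three kinds of clinical analysis:
- change described "at the four or five measurement points depending on group allocation", with means, SDs and correlations at the intermediate assessments;
- paired tests and a status for each participant: "we will use pre-post comparisons based on data from the first and last assessments to establish the status of change";
- "We will perform longitudinal analyses utilizing multilevel linear models", with covariates explored.

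On data collection, Section 3.8 says: "Following each therapeutic module, participants will complete an assessment including all outcome measures". Its tables put assessments at weeks 0, 6, 12 and 19 in the 3-module plan and at weeks 0, 6, 12, 17 and 26 in the 4-module plan. The second plan applies to the 5 to 10 who "participants will be chosen to complete the narrative exposure therapy component".

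On leaving, Section 3.9 says: "In the event of an immediate threat of suicide or the presence of severe psychotic symptoms, participants will be removed from the study". For withdrawals and removals it adds: "Data collected until that time point will be used, unless the participant requests destruction of his data".

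**The concern.** The rule in Section 3.12 suits a paired test, where a missing second score leaves nothing to analyse. It does not suit a week-6 mean, which needs only a week-6 score, or a multilevel model, which accepts incomplete series. Applied across the board, it discards usable data and turns the intermediate summaries and the models into analyses of those who reached the end.

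That group is selected. Some participants lack a post-test because the protocol itself removes them for acute risk; others may stop because they feel worse. If so, what remains looks better than the whole group did at the same visit. The scores that would show this have already been collected, and Section 3.9 says they will be used. With 20 participants and two defensible analysis sets, the choice should also be fixed before results are seen.

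**Working it through.** **1. Which analyses need both scores?**

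| Analysis (Section 3.11) | Needs pretest and post-test? | Participant without post-test under Section 3.12, read literally |
|---|---|---|
| Intermediate means, SDs, correlations | No | Excluded |
| Paired t or Wilcoxon tests | Yes | Excluded |
| First-to-last change status | Yes | Excluded |
| Multilevel models | No | Excluded |

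No clinical analysis is then left in which the Section 3.9 statement on use could be met.

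**2. What is lost per person without a post-test?** From the Section 3.8 tables, counting the baseline:
- 3-module plan: 2 of 4 assessments if the last one attended was week 6; 3 of 4 if it was week 12.
- 4-module plan: 2, 3 or 4 of 5 if the last one attended was week 6, 12 or 17.

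**3. Tilt in an intermediate mean.** Let f be the share of those with a week-6 score who have no post-test, and d the amount by which their mean week-6 change is worse than that of the others. The full mean equals the restricted mean plus f × d, so the tilt is f × d. The documents forecast neither quantity. With assumed values:
- f = 1/20, d = 0.25 SD: 0.05 × 0.25 = 0.013 SD
- f = 2/20, d = 0.5 SD: 0.10 × 0.5 = 0.05 SD
- f = 4/20, d = 1.0 SD: 0.20 × 1.0 = 0.20 SD
- d = 0: no tilt, whatever f is

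The completion bands in Section 3.11 reach down to 60%, or 8 of 20 not completing, so a larger f is not ruled out: 8/20 × 0.5 = 0.20 SD.

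**4. Tilt at the last visit.** This was simulated with four visits, equal correlation 0.6 between visits, a mean change of about −0.24 SD at the last visit, and leaving after week 6. The value 0.24 is the effect size in Section 3.11; its type is not stated, so it serves only as a yardstick.

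| Assumptions | All data | All available scores, multilevel model | Both assessments only | Overstatement |
|---|---|---|---|---|
| 6,000 simulated participants, 16% leave, odds ×3 per SD of worse week-6 change | −0.247 | −0.250 | −0.317 | 0.07 |
| Same, baseline selected above the mean | −0.563 | −0.564 | −0.614 | 0.05 |
| N = 20, about 11% leave, odds ×1.5 per SD | – | – | – | 0.02 |

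The model on all available scores recovers the full-data value without imputation; the restricted set does not. A harsher set-up gave −0.375 in the restricted set against −0.241. In it, participants had their own slopes, about 19% left after week 6 or week 12, and leaving was more strongly tied to worsening. The overstatement there is 0.13 in the units of that simulation.

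**5. Against sampling noise.** With correlation 0.6 the SD of a change score is √(2 × (1 − 0.6)) = 0.894. The mean of 20 changes has SD 0.894/√20 = 0.20. A tilt of 0.02 to 0.07 is well inside that.

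**The case against.** **The sentence may mean only the paired tests.** It speaks of one analysis and names the pretest and post-test, which fits the pre-post comparison in Section 3.11. Multilevel models do not need complete series, and Section 3.9 promises use. On this reading the sections agree. The reading is possible, but the sentence sits under a statement about statistical analyses generally and nothing limits it. It follows that a reader should not infer that the intermediate scores will certainly be discarded; the documents support only that the rule as worded would discard them.

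**Leaving therapy is not the same as missing the post-test.** This stands. The rule turns on assessment, and Section 3.12 plans follow-up of people who withdraw. Someone who stops Module 4 but attends the week-26 assessment stays in. The loss concerns only those who also miss the post-test.

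**The stakes are modest.** This stands too. These are secondary outcomes, and Section 3.1 says no efficacy conclusion can be drawn. Feasibility is counted among all who sign consent, and drop-outs are interviewed where possible.

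**Harm is not hidden.** A reader might infer that the plan cannot reveal temporary worsening, because each participant's status compares only first and last scores. The documents do not support that. Section 3.11 plans descriptions at every assessment and longitudinal models, and Section 4.2 records adverse events and checks suicidality at the intermediate assessments. A status of worsening at each visit would be a reporting preference; its absence is not an error.

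**Conclusion.** The point holds as a defect of wording with a real, probably small, analytic consequence. Section 3.12 extends a restriction that belongs to the paired comparisons to analyses that do not need it, and so conflicts with Section 3.9. The direction is towards benefit if participants without a post-test are doing worse, which is plausible for those removed for acute risk. The size cannot be derived from the documents. It is nil if missing the post-test is unrelated to symptoms and about 0.02 to 0.07 SD at the last visit under moderate assumptions. It is more under harsher ones, and up to about 0.2 SD in an intermediate mean. All of this rests on assumed dropout and is hard to distinguish from noise with 20 participants. The case for changing the text is that the change costs almost nothing, removes an internal conflict and fixes the analysis set in advance. It does not rest on any demonstrated large bias.

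**What to change.** Amend Section 3.12 before the data are analysed:

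1. Apply the both-assessments restriction only to the paired tests and the first-to-last change status.
2. Include every participant with a baseline and at least one later assessment in the descriptive summaries, in line with Section 3.9 and subject to any request to destroy data.
3. Fit the multilevel models to all available assessments, without imputation.
4. Print n at each assessment.

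The cost is a few sentences of SAP text and one extra row per table, with no new visits or measures. There are limits. Visit means will rest on different numbers of people, which is why n must be shown. The models still assume that leaving depends only on observed scores, which is doubtful when an acute crisis arises after the last assessment. The paired tests remain an analysis of those with both scores and should be read beside the model estimate.

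Optionally, plot individual trajectories by code, without demographic detail, marking where participants left. This would make temporary worsening easy to see; leaving it out is not an error in the plan.
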